1.3 Rationale for the current study and proposed vaccine schedule

The superior responses to rPT-containing BNA vaccines observed in Thai adults and adolescents strongly suggest a higher immunogenicity of the BNA genetically-detoxified rPT antigen. Importantly, however, this superior immunogenicity was observed in adults (Phase I/II) and adolescents (Phase II/III) who had been primed as infants with whole-cell pertussis vaccines – i.e. with inactivated vaccines containing native PT. In Switzerland, Europe and the US, the use of whole-cell vaccines for pertussis priming was replaced in 2000 by the use of the better tolerated acellular vaccines – which contain chemically-detoxified PT (aP).

A previous Geneva study (Blanchard [name] et al. CID 2019) reported that boosting aP-primed adolescents with one dose of the rPT-containing vaccine (Pertagen®) was well tolerated and elicited 2-fold stronger anti-PT neutralizing and binding antibody responses than a sixth dose of cd/Tdap. However, this superior immunogenicity was found to be transient; a potential solution being repeat doses of the rPT-containing BNA vaccine.

[figure not shown]

Figure 3. Antibody responses to recombinant acellular pertussis vaccine (r-aP Pertagen®) compared to the standard vaccine containing chemically detoxified pertussis toxin (cd/Tdap Boostrix®)

[figure not shown]

Figure 4. Memory B-cell response to recombinant acellular pertussis vaccine (r-aP Pertagen®) compared to the standard vaccine containing chemically detoxified pertussis toxin (cd/Tdap Boostrix®)

The critical question to be addressed here is whether two doses of rPT/FHA will prove to be more effective than one dose in adults previously exposed to at least 5 doses (2 months, 4 months, 12 months, 4-7 years and 11-14/15 years) of chemically-detoxified PT-containing vaccines. This question is fundamental to define the potential of repeat doses of rPT/FHA to overcome the limited and rapidly waning efficacy of PT-containing boosters in adults.

We therefore propose to assess the safety and immunogenicity of two doses of BNA aP (Pertagen®) administered at a 6 month interval to adults 18-30 years old previously primed with 5 doses of chemically-inactivated acellular pertussis vaccines and to compare the results with responses elicited by a single dose of BNA aP (Pertagen®) in the same population.

2 OBJECTIVES AND ENDPOINTS

2.1 Primary objective

The primary objective is to assess the immunogenicity of two doses compared to a single dose of an acellular pertussis vaccine (Pertagen®) including genetically-detoxified pertussis toxin (rPT) administered at 6 months interval and delivered by the intramuscular route to adults aged 18-30 years previously primed and boosted with chemically-detoxified PT.

2.1.1 Primary outcome measures

The main immunogenicity endpoints will be the geometric mean concentration (GMC) of neutralizing antibodies to PT.

2.2 Secondary objectives

- To assess the safety of two doses at 6 months interval of intramuscular immunization with Pertagen® administered to adults, compared to one dose of Pertagen®.
- To assess the humoral responses elicited by two doses of Pertagen® when administered to adults, compared to one single dose.

2.2.1 Safety outcome

Genetically detoxified rPT was proven safe in several clinical trials (see 1.2 Clinical development of aP vaccines including genetically-detoxified PT).

Solicited local and systemic reactions will be recorded on a diary card during 7 days and unsolicited AEs for 28 days after immunization.

2.2.2 Main secondary immunogenicity outcomes

The following parameters will be assessed at Day 0, Day 28 and Month 6 post first and second vaccination:

- Geometric mean concentrations (GMCs) of PT, FHA, tetanus and diphtheria-toxoid specific IgG antibodies measured by ELISA.
- Seroresponse rates of PT, FHA, tetanus and diphtheria-toxoid specific IgG antibodies measured by ELISA.
- Seroresponse rates of PT specific neutralizing antibodies.

2.3 Exploratory Outcomes Measures

Exploratory immunological measures will be performed at each visit pending sufficient or additional funding.

These are anticipated to include:

- The assessment of antibody titers to specific neutralizing and non-neutralizing epitopes of PT, by competitive ELISA, following one for two doses of Pertagen®
- To compare antibody avidity following one or two doses of Pertagen®
- To assess the frequency and phenotype of PT-specific memory B cell responses following one or two doses of Pertagen®

Exploratory immunological measures and the quantification of neutralizing anti-PT antibodies will involve collaboration with other specialized laboratories and research groups in Switzerland and/or abroad. This will involve transfer of coded serum/plasma and/or frozen peripheral blood mononuclear cells (PBMC) samples, traceable only by means of a subject identifier and as described in the signed informed consent form.

3 CLINICAL STUDY MATERIALS

3.1 Study vaccines

Two vaccines will be used in the study. The BNA study vaccine (Pertagen®) and the control vaccine (Revaxis®).

Group A	Revaxis® + Pertagen®	50 subjects
Group B	Pertagen® + Pertagen®	50 subjects

Table 1. Study groups

	Pertagen®	Revaxis®
Active substance		
Tetanus Toxoid (TT)	-	NLT 20IU
Diphtheria Toxoid (DT)	-	NLT 2.0 IU
Pertussis Toxoid (PT)	5 µg ^a	-
Filamentous Hemagglutinin (FHA)	5 µg	-
Pertactin (PRN)	-	-
Fimbriae type 2/3	-	-
Inactivated polio viruses type 1-2-3	-	40U (type 1), 8U (type 2), 32U (type 3)
Adjuvants		
Aluminum Hydroxide	0.3 mg/dose	0.35mg/dose
Volume for Injection	q.s. to 0.5 mL	q.s. to 0.5 mL
a: Recombinant Pertussis Toxin (rPT)		

Table 2. Vaccine composition of each dose of 0.5 mL presented in pre-filled syringe

The investigational product Pertagen® will be manufactured, labeled, packaged and released for clinical use by BNA, in accordance with the requirements of Good Manufacturing Practices. The quality control standards and requirements for the investigational vaccine will be described in separate release protocols and the required approvals will have been obtained. One batch will be used for the entire study.

The Revaxis® vaccine used in this study is commercially available in Switzerland and will be purchased for the study. One batch will be used for the entire study.

3.2 Packaging, Labeling, and Storage of Vaccines

Study vaccines will be provided in appropriate boxes.

The investigational vaccine container and the syringe labels will contain the following information: Sponsor name, protocol number, vaccine code, storage instructions, and **“For Clinical Study Use Only”**. The licensed vaccines will be re-labeled according to the applicable local requirement.

All study products will be stored in a safe, locked, and secure place with no access by unauthorized personnel. They will be kept in a refrigerator (+2°C to +8°C) and **not be frozen**. Storage temperature will be monitored every day.

3.3 Preparation and Administration

Both Pertagen® and Revaxis® vaccines are presented in 0.5 mL pre-filled syringes to be administered by intramuscular injection in the non-dominant deltoid.

The package containing the used syringe (empty syringe), and any vaccine dispensing form / document (if applicable) will be stored at study site until end of the study.

3.4 Clinical Study Supply, Dispensing, and Accountability

All study products will be provided by BNA and shipped to the study site. Shipment content and condition (including temperature control) will be checked at reception. All study products used in the study will be accounted for in a Study Vaccine Accountability Record indicating the date of administration to the subject.

An additional quantity of each vaccine will be supplied. In case a syringe of vaccine is broken or unusable, the unblinded site staff will replace it. Documentation of the use of the replacement syringe and reason for using it will be recorded by the site staff.

At the end of the study, all unused vaccines will be, at BNA's option, either returned to BNA or destroyed in accordance with written instructions provided by BNA. If to be returned, a shipment will be recorded, identifying each syringe being included in the shipment. The used study vaccines will be destroyed at study site according to the procedure of study site institution.

4 STUDY DESIGN

4.1 Overall Study Design

This is a phase II/III randomized, double-blind controlled study to compare the safety and immunogenicity of 1 or 2 doses of acellular pertussis vaccines containing genetically-detoxified pertussis toxin in adults aged 18-30 years, previously primed and boosted with acellular pertussis vaccines.

[figure not shown]

Figure 1. Study Flow Chart

4.2 Study population and entry criteria

The study population will include adults aged 18-30 years previously primed and boosted with acellular pertussis vaccines (see entry criteria below).

A leaflet describing the study objectives and modalities will be prepared to advertise the study to medical students of the University of Geneva, as well as other faculties if deemed necessary. An email containing the same information will also be sent out to the students' mailing list. Potentially interested volunteers will be invited to contact the study staff.

4.2.1 Informed consent

The participant information form will be made available to these potential volunteers in advance such that they have ample time and opportunity to inquire about details of the trial and to decide whether or not to participate. Consenting participants must sign and date the informed consent form before any study-specific procedures may be performed.

At the first visit, the volunteer will be fully informed of all aspects of the trial, the potential risks and their obligations. The following general principles will be emphasized:

- Participation in the study is entirely voluntary;
- Refusal to participate involves no penalty or loss of medical benefits;
- The volunteer may withdraw from the study at any time, without supplying a reason for withdrawal;
- The volunteer is free to ask questions at any time to allow him or her to understand the purpose of the study and the procedures involved;
- The study involves research on an investigational vaccine;
- The volunteer's primary care practitioner may be contacted to corroborate their medical history or seek additional information;
- The volunteer's blood samples taken as part of the study will be anonymized and stored for a period of 15 years.

The aims of the study and all tests to be carried out will be explained. The volunteer will be given the opportunity to ask about details of the trial, and will then have time to consider whether or not to participate. If the volunteer does decide to participate, he or she will sign and date two copies of the consent form, one for his/her personal records, and one to be stored at site in the source documents. These forms will also be signed and dated by the Investigator.

4.2.2 Inclusion and exclusion criteria

This study will be conducted in adults aged 18-30 years, who meet the following inclusion and exclusion criteria:

Inclusion criteria

The volunteer must satisfy the following criteria to be eligible for the study:

- Has provided written informed consent before enrollment;
- Male or female, ages 18-30 years (inclusive) at the time of enrollment;
- With documented history of acellular pertussis immunization (5 doses);
- Free of clinically significant health problems, as determined by pertinent medical history and clinical examination at study screening;
- Non-pregnant, non-lactating female :

- This implies a negative urinary pregnancy test at enrolment;
- If sexually active, female subjects must be willing to use reliable birth control measures for 1 month after vaccination;
- Able to attend all scheduled visits and to understand and comply with the study procedures.

Exclusion criteria

The volunteer may not enter the study if any of the following apply:

- Prior dTpa immunization within the last 5 years or prior dT immunization within the last 2 years, or any other investigational vaccine likely to impact on interpretation of the trial data, as judged by the Principal Investigator;
- Suspected or confirmed pertussis infection within the last 10 years or documented pertussis infection in a household member within the last 10 years;
- History of severe local or systemic reactions to any vaccination or a history of severe allergic reactions;
- Known hypersensitivity or allergy to diphtheria, tetanus, or pertussis vaccine (including excipients);
- Receipt of investigational product up to 30 days prior to enrollment or ongoing participation in another interventional clinical trial;
- Receipt of licensed vaccines within 30 days of planned study immunization or ongoing participation in another clinical interventional trial;
- Acute or chronic, clinically significant psychiatric, hematologic, pulmonary, cardiovascular, or hepatic or renal functional abnormality as determined by the Investigator based on medical history, physical exam;
- Any confirmed or suspected immunosuppressive or immunodeficient condition, including human immunodeficiency virus (HIV) infection, asplenia, cytotoxic therapy in the previous 5 years, and/or diabetes;
- Any chronic or active neurologic disorder, including seizures, and epilepsy, excluding febrile seizures as a child;
- Has a known history of vaccine-induced Guillain-Barré Syndrome;
- Has an active malignancy or recent (<10 years) history of metastatic or hematologic malignancy;
- Suspected or known alcohol and/or illicit drug abuse within the past 5 years;
- Pregnant or lactating female, or female who intends to become pregnant during the study period;
- Administration of immunoglobulins and/or any blood products within the 120 days preceding study entry or planned administration during the study period;
- Receipt of chronic (>14 days) immunosuppressants or other immune-modifying drugs within 6 months of study entry:
 - For corticosteroids, this will mean prednisone or equivalent ≥ 0.5 mg/kg/day,
 - Intranasal and topical steroids are allowed;
- Any other significant finding that, in the opinion of the investigator, would increase the risk of the individual's having an adverse outcome by participating in this study.

Temporary exclusion criteria at the time of randomization

The following criteria constitute contraindications to administration of vaccine at that point in time; if any one of these occurs at the time scheduled for randomization, the subject may be randomized at a later date without the need for re-screening, at the discretion of the Investigator, or withdrawn at the discretion of the Investigator:

- Acute disease at the time of randomization. (Acute disease in the context of this trial is defined as the presence of a moderate or severe illness with or without fever.) The vaccine/placebo can be administered to persons with a minor illness such as mild upper respiratory tract infection with or without low-grade febrile illness, i.e. temperature of $\leq 37.5^{\circ}\text{C}$;
- Body temperature $\geq 38^{\circ}\text{C}$ within 3 days of the intended vaccination;
- Any other significant finding that, in the opinion of the investigator, would temporarily increase the risk of the individual's having an adverse outcome by participating in this study.

4.2.3 Compliance with dosing regimen

The first intervention (study vaccine Pertagen® or Revaxis®) will be administered by the Clinical Investigator at Day 0, and the second (Pertagen®) at Day 180. At no time will the study medication be in the possession of the volunteer; compliance will not, therefore, be an issue.

4.3 Randomization

At Day 0, eligible subjects will be randomized in a 1:1 ratio into one of the following vaccine groups:

Group A	Revaxis® + Pertagen®	50 subjects
Group B	Pertagen® + Pertagen®	50 subjects

Table 1. Study groups

Randomization procedure

Randomization allocation will be performed on a 1:1 basis generated by computer randomization, with a 10-block size, concealed in sequentially labeled opaque envelopes. Each participant will be assigned a unique treatment number that corresponds to his or her treatment allocation. Only the unblended immunizing nurses will have access to the treatment allocation.

Randomization of subjects to treatment will occur at Visit 1 after all entry procedures have been performed and eligibility for the study confirmed. 100 volunteers will be allocated to either Group A or Group B at the ratio of 1:1 and will receive a 3-digit subject number preceded by the acronym of the study site (GE- _ _). The 3-digit subject number will be assigned according to the participant's chronological order of enrollment at the site. The subject number will be used as the subject identifier throughout the study.

Each participant will be randomized following the randomization list by chronological order and will be immunized according to the vaccine group assignment.

Participants will be blinded in order to keep the double-blind design of the study.

The personal responsible for study vaccine preparation, handling, storage and accountability, as well as immunization will be unblinded.

The team responsible for assessing adverse events will be blinded.

The laboratory staff performing the immunological assays will also be blinded.

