SECONDARY OBJECTIVES:	
 To assess the safety of two doses at 6 months interval of intramuscular immunization with Pertagen® administered to adults as compared to one dose of Pertagen®. To assess the humoral responses elicited by two doses of Pertagen® as compared to a single dose. The following parameters will be assessed at Day 0, Day 28 and Month 6 post first and second vaccination: 
 Geometric mean concentrations (GMCs) of PT, FHA, tetanus and diphtheria-toxoid specific IgG antibodies measured by ELISA Seroresponse rates of PT, FHA, tetanus and diphtheria-toxoid specific IgG antibodies measured by ELISA Seroresponse rates of PT, FHA, tetanus and diphtheria-toxoid specific neutralizing antibodies.

PHASE II/III Pertagen2x VACCINE TRIAL: PROTOCOL v1.2

PROTOCOL SYNOPSIS – PHASE II/III 2 doses rPT-VACCINE TRIAL

EXPLORATORY OBJECTIVES:

- To assess antibody titers to specific neutralizing and non-neutralizing epitopes of PT, by competitive ELISA, following one or two doses of Pertagen®
- To compare antibody avidity following one or two doses of Pertagen®
- To assess the frequency and phenotype of PT-specific memory B cell responses following one or two doses of Pertagen®

STUDY POPULATION: Volunteers, 18-30 years of age

NUMBER OF SUBJECTS: 100 (50 subjects per each vaccine group)

PHASE II/III Pertagen2x VACCINE TRIAL: PROTOCOL v1.2

PROCEDURE AND FOLLOW-UP:

This is a phase II/III, single center, randomized, double-blind controlled vaccine trial in 18 to 30 years old volunteers. It will be performed at the Plateforme de Recherche Clinique de Pédiatrie, Gynécologie et Obstétrique (PGO) of the HUG.

Volunteers who have signed the informed consent and who gave their written assent will be screened clinically for general health status and those who fulfill all exclusion and inclusion criteria will be enrolled into the study.

At Day 0, eligible volunteers will undergo a venous bleed for the determination of baseline values and enter the randomization scheme, being allocated to one of two groups: A (Revaxis® + Pertagen®), B (Pertagen® + Pertagen®) (Tables 1 and 2).

Group A	Revaxis® + Pertagen®	50 subjects
Group B	Pertagen® + Pertagen®	50 subjects

Table 1. Study groups

	Pertagen®	Revaxis®
Active substance		
Tetanus Toxoid (TT)	-	NLT 20IU
Diphtheria Toxoid (DT)	-	NLT 2.0 IU
Pertussis Toxoid (PT)	5 µg ^a	-
Filamentous Hemagglutinin (FHA)	5 µg	-
Pertactin (PRN)	-	-
Fimbriae type 2/3	-	-

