5 CONDUCT OF STUDY

5.1 Study visits

Participants will be asked to attend 5 scheduled visits at the Plateforme de Recherche Clinique de Pédiatrie, Gynécologie et Obstétrique (PGO) of the HUG. All subjects will be asked to remain in the study throughout its entire duration (one year). If a subject does not appear at a scheduled visit, every effort will be made to contact him or her to confirm that she/he is well and to reschedule the visit. This effort will be documented into the source data. Each study visit is described in detail below. An overview is found in Schedule of Assessment.

Each visit is assigned a time point and a window period within which the visit will be conducted. Deviations from the window periods are to be avoided; however in some exceptional situations, they are permitted at the discretion of the Principal Investigator in the interest of completing the study schedule and obtaining subject safety and immunogenicity evaluations.

5.1.1 Visit 1: Randomization, assessment and immunization, Day 0

Adults aged 18-30 years, male and female with no significant medical history or active illness will be recruited by the clinical investigators.

Volunteers who consented and who have signed the informed consent will be screened for eligibility.

The following activities will be performed during the first visit:

- Informed consent form (ICF) will be provided:
 - The volunteer will be allowed sufficient time for questions and answers and reflection as to whether or not they wish to participate; no further activity will take place until signing of ICF;
- Inclusion and exclusion criteria will be evaluated;
- Demographic data (including sex, birthdate, race) will be recorded;
- The medical history (including potential concomitant medication) will be reviewed;
- The female participants will be informed that the study is not open to subjects whom may be or become pregnant. A urinary pregnancy test will be performed and enrollment only confirmed if negative. They will also be reminded of the need to use birth control measures in case of sexual intercourse.
- In all subjects a physical examination will be performed (subject's general appearance, skin, respiratory and cardiovascular function), as well as vital signs (blood pressure, heart rate, temperature, respiratory rate), weight, and height.

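### Section 4.3 discloses one fixed block size of 10 at a single site with unblinded immunizers; if the recruiter is also the immunizer, as 4.2.3 and 5.1.1 together imply but 4.3 denies, up to 1 in 6 assignments can be foreseen with certainty

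*Combined protocol and SAP*

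**What the plan says.** Section 4.3 gives the allocation method: "Randomization allocation will be performed on a 1:1 basis generated by computer randomization, with a 10-block size, concealed in sequentially labeled opaque envelopes". It is the only block size in the document, and neither varying sizes nor stratification is mentioned. The synopsis describes the trial: "This is a phase II/III, single center, randomized, double-blind controlled vaccine trial in 18 to 30 years old volunteers". Section 4.3 adds that "100 volunteers will be allocated to either Group A or Group B at the ratio of 1:1", that "Each participant will be randomized following the randomization list by chronological order", and that "The 3-digit subject number will be assigned according to the participant's chronological order of enrollment at the site".

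On blinding, 4.3 says: "The personal responsible for study vaccine preparation, handling, storage and accountability, as well as immunization will be unblinded". It also says that only the immunizing nurses can see the allocation, and that the adverse-event assessors and the laboratory staff are blinded. Section 6.4 holds the codes apart from the investigators who assess adverse events.

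Two other sections do not fit with this. Section 4.2.3 says: "The first intervention (study vaccine Pertagen® or Revaxis®) will be administered by the Clinical Investigator at Day 0". Section 5.1.1 says: "Adults aged 18-30 years, male and female with no significant medical history or active illness will be recruited by the clinical investigators".

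Randomization takes place after eligibility has been confirmed (4.3). Section 4.2.2 leaves one exclusion criterion to the investigator's opinion and lets the investigator postpone randomization to a later date.

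**The concern.** In a balanced block of known length, the assignments still to come depend on those already made. Once one arm has used its five places, every remaining place in the block belongs to the other arm. Opaque envelopes do not prevent this, because the forecast comes from counting past assignments and needs no envelope to be opened. Subject numbers follow enrolment order, so GE-001 to 010, 011 to 020 and so on mark the blocks, apart from any shift caused by replacements under 6.3.

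What matters is whether anyone who knows the past assignments can also influence who is enrolled next. Such a person could use the investigator's discretion in 4.2.2, knowingly or not, to admit, exclude or postpone a volunteer in the light of the coming assignment. That is selection bias, and randomization would no longer protect the comparison for the volunteers concerned.

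A disclosed block also weakens the blind slightly. If one code is broken (6.4, 7.7.2), the other nine members of the block can be identified by number, and the odds on their assignments are no longer even.

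**Working it through.** **Inputs.** Block size 10, ratio 1:1, total 100, one chronological list (all 4.3); one site (synopsis). The protocol gives no figure for predictability.

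**The plan's own figure.** 100 / 10 = 10 complete blocks. Each holds 5 + 5, so the total is 10 × 5 = 50 per group, as stated.

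**Assignments known with certainty.** Take an observer who knows the block size and every earlier assignment in the block. The known assignments are the final run of one arm. Of the C(10,5) = 252 possible blocks, the number ending in a run of exactly k is 2 × C(9−k, 4):

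| k known | blocks | probability |
|---|---|---|
| 1 | 140 | 0.556 |
| 2 | 70 | 0.278 |
| 3 | 30 | 0.119 |
| 4 | 10 | 0.040 |
| 5 | 2 | 0.008 |

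Expected number known per block = (140×1 + 70×2 + 30×3 + 10×4 + 2×5) / 252 = 420 / 252 = 1.67. The closed form for a block of 2m agrees: 2m/(m+1) = 10/6. As a share this is 1/(m+1) = 1/6 = 16.7%, or 16.7 of 100 assignments. At least the last assignment in every block is known. Simulation of 100-person lists gave 16.7%.

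**Best guess.** Always guessing the under-filled arm is right for 65.3% of assignments over the 252 blocks, against 50% by chance.

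**Who could hold this knowledge.** There are two readings:

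- *4.2.3 with 5.1.1:* the Clinical Investigator injects and the clinical investigators recruit. Under 4.3 whoever injects is unblinded, so the recruiter knows the past assignments and the 1/6 applies.
- *4.3 alone:* only nurses know the assignments, and no section gives nurses a part in recruitment, eligibility or deferral. If the blind holds, a recruiter knows no past assignment and can foresee none with certainty. The nurses could still foresee 1 in 6, and the figure reaches a recruiter only if they share what they know.

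**One broken code.** If one member of a block is revealed as arm A, 4 A and 5 B remain among the other nine. Each of these has probability 5/9 = 55.6% of being B, against 50% before.

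**With varying blocks.** Assumed for illustration: sizes 8, 10 and 12 drawn at random, and an observer who knows all past assignments and also this set of sizes. Simulation that tracks every block boundary still possible gave about 1.3% of assignments known with certainty, and about 65% correct by best guess. From 16.7% to 1.3% is roughly a twelvefold reduction. The certain share is lower still if the set of sizes is secret.

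**The case against.** The strongest reply is that 4.3 is the section that governs allocation, and it confines knowledge of assignments to the immunizing nurses. The recruiter who also immunizes appears only when a sentence from the compliance section (4.2.3) is joined to one from 5.1.1. Under 4.3 as written, selection bias would require nurses to pass on allocations, and nothing in the documents suggests that they would. This part of the reply stands. A reader might infer that recruiters will know 1 assignment in 6. The documents do not support that without the condition that 4.2.3 is followed or that nurses share what they know.

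The second reply is that the consequences are limited. The primary endpoint is a neutralization assay read by blinded laboratory staff, the adverse-event team is blinded, the safety analysis is descriptive, and p-values are exploratory (8.1). All participants receive Pertagen at Visit 3, so there is no evident motive to steer healthy volunteers to one arm. A single code break moves the odds only from 50% to 55.6%. This also stands, and it keeps the point at moderate weight. A reader might go on to infer that the primary titres are biased, but nothing in the documents shows that.

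The third reply is that confirming eligibility before randomization closes the gap. This does not stand. The forecast is available before eligibility is judged, so it can affect that decision or the decision to postpone.

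Finally, varying block sizes do not make assignments unpredictable. They remove almost all certainty, but the best-guess rate is nearly unchanged.

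**Conclusion.** The point holds in conditional form. A single fixed block size is disclosed in the protocol of a one-site trial with unblinded preparers and immunizers. Concealment then rests wholly on a separation of roles about which 4.2.3, 4.3 and 5.1.1 disagree.

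The size is exactly 1/6 (about 17 of 100 assignments) for someone who knows the block size and all earlier assignments in the block. For recruiters this is an upper figure that applies under 4.2.3 with 5.1.1, or if nurses share what they know. It is zero certain assignments if 4.3 governs and the blind holds. The exposure is mainly to baseline comparability and the adverse-event comparison. The documents do not show that foreknowledge has been or would be used. The change is worth making because it is cheap and protects the trial under either reading.

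**What to change.** Before the list is used:

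1. In 4.3, replace the stated block size with wording such as: *randomly varying block sizes that are not disclosed to site staff and are recorded only in a restricted document held by the person who generates the list*.
2. Reconcile 4.2.3, 4.3 and 5.1.1 on who immunizes.
3. State in 4.3 that unblinded staff do not recruit, judge eligibility or decide on deferral.

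The cost is a regenerated list and set of envelopes and a few sentences of text, with no extra visits or participants. The drawback is that the groups may differ slightly from 50:50 if the last block is incomplete. With a largest block of 12, one arm can lead by at most 6 when enrolment stops at 100, so the worst case is 53:47.

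The documents do not say whether enrolment has begun. If it has, the fix is limited to the role-separation sentence and, where possible, varying blocks for the remaining envelopes.
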